# Evaluating an Online, Single-Session Intervention Targeting Self-Injurious Behavior in Adolescents

**Data Collection Status:** Have any data been collected for this study already? Note: 'Yes' is a discouraged answer for this pre-registration form.

No data has been collected already for this study.

## What's the main question being asked or hypothesis being tested in this study?

To determine whether participants randomized to an online single session intervention (SSI) targeting non-suicidal self-injurious behavior ("Project SAVE") endorse:

1. Lower self-reported *likelihood* of future non-suicidal self injury immediately post-intervention (secondary outcome)
2. Lower self-reported *frequency* of suicidal ideation (in the past 3 months) at 3 month follow-up (secondary outcome)
3. Lower self-reported *frequency* of non-suicidal self-injury (in the past 3 months) at 3 month follow-up (primary outcome)

relative to those randomized to an active control condition (i.e. supportive therapy SSI; Schleider & Weisz, 2018) in a large sample of cisgender heterosexual & sexual and gender minority teenagers ages 13-16 years old.

## Describe the key dependent variable(s) specifying how they will be measured.

Our primary and secondary dependent variables will be measured using the self-report version of the Self-Injurious Thoughts and Behaviors Interview-R (SITBI-R; Fox, Harris, Wang, Millner, Deming, & Nock, 2020). Items in this measure ask participants about their attitudes/beliefs/history concerning various self-injurious thoughts and behaviors, including suicidal ideation (SI) and non-suicidal self-injury (NSSI). While our participants will complete all questions from the SITBI-R, the present study evaluates items that measure past 3-month frequency of NSSI, past 3-month frequency of SI, likelihood of future NSSI (see below section).

[https://shirleywang.rbind.io/papers/Fox\\_psychassess\\_2020.pdf](https://shirleywang.rbind.io/papers/Fox_psychassess_2020.pdf)

## Primary Dependent Variable

**NSSI Frequency in the Past 3 Months.** Our primary outcome variable will compare past 3-month NSSI frequency at 3-month follow-up—for participants assigned to the Project SAVE SSI versus supportive therapy SSI (i.e. control condition). At pre-intervention and 3-month follow-up time points, participants will indicate "how many times they have purposely hurt themselves without wanting to die" in the past 3 months in an open-response text box. Notably, in the present study's survey flow, this question is displayed following display logic—such that

participants endorsing zero NSSI in the past 3-months (via a previous question) skip to the end of the question block and are not prompted to answer our main frequency outcome question. For these individuals, we will impute a past 3-month frequency value equal to 0 (as they have endorsed zero NSSI in the previous 3 months in the earlier question). More information about how we will handle very large numbers (i.e. outliers) for this outcome is reported below (see “Outliers and Exclusions” section; “Winsorizing Outliers” subsection).

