### ***Imputing Data***

After excluding individuals based on the above criteria, we will impute any missing data in our variables of interest (pre- and post-intervention likelihood of future NSSI; pre- and post-intervention desire for future NSSI; past 3-month frequency of NSSI at pre-intervention and follow-up). To do this, we will execute an expectation-maximization and bootstrapping algorithm via the Amelia II package in R (Honaker, King, & Blackwell, 2011; <https://cran.r-project.org/web/packages/Amelia/Amelia.pdf>). All variables from the corresponding statistical model (i.e. hypothesis tests 1 - 3) will be included in the algorithm used to create the imputed data for that test: (a) baseline values for the outcome—likelihood of NSSI, desire for NSSI, or past 3-month frequency of NSSI, (b) follow-up values for the outcome, and (c) condition assignment, as well as (d) other baseline variables that are likely associated with each outcome variable (for **past 3-month frequency of NSSI at follow-up**: lifetime history of NSSI (y/n), past-month frequency of NSSI, past-year frequency of NSSI, and lifetime frequency of NSSI at baseline; for **likelihood of NSSI post-intervention**: all of these same variables plus past 3-month frequency of NSSI at baseline; for **past 3-month frequency of SI at follow-up**: lifetime history of SI (y/n), past-month frequency of SI, past 3-month frequency of SI, past-year frequency of SI, and lifetime frequency of SI at baseline). Together, these variables (a - d) will be used to create the imputed datasets for each of our three hypotheses.

The number of imputed datasets we create will equal the percentage of missing data for each of our three outcome variables (post-intervention likelihood of NSSI, post-intervention desire for future NSSI, past 3-month frequency at follow-up), rounded up to the next integer value. For example, we will create 7 imputed datasets to test hypothesis 1 if 6.2% of the data for the post-intervention likelihood of NSSI outcome variable is missing. We will create 8 imputed datasets to test hypothesis 2 if 7.6% of the data for the post-intervention desire for future NSSI outcome variable is missing.

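### A follow-up report of NSSI is not carried into the imputation of the primary count, so a youth who reported self-injury but gave no usable number can be imputed 0 or a negative value

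*Combined protocol and SAP*

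**What the plan says.** The section on the primary dependent variable describes two linked items. An earlier question asks whether any NSSI occurred in the past 3 months, and "participants endorsing zero NSSI in the past 3-months (via a previous question) skip to the end of the question block". Everyone else is asked how often, "in the past 3 months in an open-response text box". The earlier answer is then used for one purpose: for those who denied NSSI, "For these individuals, we will impute a past 3-month frequency value equal to 0".

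Under Imputing Data, the plan states: "After excluding individuals based on the above criteria, we will impute any missing data in our variables of interest". The method is given as "we will execute an expectation-maximization and bootstrapping algorithm via the Amelia II package in R". On the contents of the model it says "All variables from the corresponding statistical model (i.e. hypothesis tests 1 - 3) will be included in the algorithm used to create the imputed data". These are the baseline outcome, the follow-up outcome and condition. The extra variables for the primary outcome are "lifetime history of NSSI (y/n), past-month frequency of NSSI, past-year frequency of NSSI, and lifetime frequency of NSSI at baseline". All of these extras are baseline variables. The follow-up screening answer is not among them, and no lower bound, transformation or rounding is stated.

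Three other places bear on the point. Type 2 Exclusions removes participants who give random text in open responses. Winsorizing Outliers trims only values above the 95th percentile. The tests of hypotheses 2 and 3 choose among Poisson, negative binomial and the zero-inflated form of each.

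**The concern.** A youth who answers the follow-up screen with a yes has told the trial that the count is at least 1. If the number is then blank, or is text that cannot be read as a number, the plan treats the count as missing and discards that information. The imputation is fitted to all responders, including those coded 0, and draws from an unbounded normal model. Followed as written, it can return a value that contradicts the youth's own answer.

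This concerns the primary outcome. Imputed counts for such youths are too low on average, and some are negative. The planned count models cannot take negative values, so the analyst would have to choose a repair after seeing the data. The supplementary run on non-imputed data does not settle the matter, because it drops these youths and keeps every observed zero.

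**Working it through.** The plan gives no mean, SD, share of zeros, baseline correlation or rate of unusable answers, so there is no planned figure to reproduce. Everything from step 2 on rests on stated assumptions.

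**1. Trace each follow-up pattern through the plan.**
- Screen no: count set to 0.
- Screen yes, usable number: that number.
- Screen yes, no usable number: excluded if judged random text; otherwise imputed without the yes.
- No screening answer (lost to follow-up, or stopped before it): imputed. Here the unconditional model conflicts with no answer that the trial holds.

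Only the third pattern is at issue.

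**2. Chance that a normal draw is 0 or below.** P(draw ≤ 0) = Φ(−mean/SD) = Φ(−1/CV), where CV is the coefficient of variation of the imputation distribution.
- CV 0.6: Φ(−1.67) = 5%
- CV 0.8: Φ(−1.25) = 11%
- CV 1.0: Φ(−1.00) = 16%
- CV 1.5: Φ(−0.67) = 25%
- CV 2.0: Φ(−0.50) = 31%

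A share of 20% needs mean/SD = 0.84, that is CV = 1.19.

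**3. Simulated share for screen-positive youths.** Assumptions: 10%, 25% or 40% zeros at follow-up; positive counts equal to 1 plus a gamma-Poisson variable with mean 8 or 15 and shape 0.4, 0.8 or 1.5; latent correlation with baseline 0.3 or 0.6. Imputation was a normal regression on the baseline count, which approximates Amelia II; condition, the other auxiliary variables and the bootstrap step were left out. Shares of draws at 0 or below:
- Raw scale: 13% to 33% (median 23%)
- Winsorized first: 11% to 28% (median 21%)
- log(1 + count) scale, which the plan does not state: 2% to 20% (median 10%)
- Screening answer added as a predictor, still without a bound: 4% to 24% raw, 2% to 20% winsorized first, 0% to 3% on the log scale

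**4. Effect on arm means.** Assume 70% report NSSI at follow-up and 10% of those give no usable number, so 0.70 × 0.10 = 7% of responders are affected. In a simulation of this case (n = 500), 21.5% of rounded draws were 0 or below, and the imputed mean was 7.65 against a true 10.62.
- Shortfall with negatives left in: 10.62 − 7.65 = 2.97 (28%). The arm mean is 0.70 × 10.62 = 7.43, so 0.07 × 2.97 / 7.43 = 2.8%.
- Shortfall with negatives set to 0: 21.5% below 0.5 implies SD = (7.65 − 0.5)/0.789 = 9.06. The mean becomes 7.65 × 0.801 + 9.06 × 0.279 = 8.66. The shortfall is 1.96 (18%), and 0.07 × 1.96 / 7.43 = 1.8% of the arm mean.

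**5. Effect on the rate ratio (true value 1.00).** With equal unusable rates both arms fall by the same proportion and the ratio stays near 1.00. With 5% against 15% unusable, the affected shares are 0.035 and 0.105. With negatives set to 0:
- (7.43 − 0.035 × 1.96) / (7.43 − 0.105 × 1.96) = 7.36 / 7.22 = 1.02

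Simulation of this 5% against 15% case gave a shift of about 0% to 2%. Leaving negatives in would give 7.33 / 7.12 = 1.03, but the count models could not be fitted to such data. For the supplementary non-imputed run, with an assumed mean of 10 among positives, the means are 6.65/0.965 = 6.89 and 5.95/0.895 = 6.65, a ratio of 1.04.

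**6. Comparison of remedies.** In a base case with a true mean of 10.7 for the affected youths, truncating raw-scale normal draws at 1 gave 12.1. Drawing from responders with a positive count gave 10.5.

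**The case against.** The strongest reply is that the gap is narrow and its consequence for the comparison is not shown. Most of that stands.
- A reader might infer that these youths are imputed as if nothing were known about them. They are not: the baseline count, the NSSI history and condition are all used. Only the follow-up yes is lost.
- A reader might take every missing count to belong to a known self-injurer. The documents do not say so: youths lost to follow-up, or who leave the screen unanswered, also lack a count.
- Some unreadable text would be excluded as random text and never imputed. Blanks and verbal quantities are not clearly covered by that rule.
- Part of the share at or below 0 comes from unbounded normal draws for a skewed count, not from omitting the screen. Step 3 confirms this: adding the answer as a predictor does not by itself remove the problem on the raw scale.
- It is tempting to say that false zeros distort the choice between zero-inflated and other models. In the step 4 case they add 0.215 × 7% = 1.5 percentage points to a 30% zero share, and no change in the selected model has been shown.

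None of this supplies the missing rule. The plan still permits imputed values that an answer in hand rules out.

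**Conclusion.** The point holds as a minor gap in the handling of the primary count. For youths who report NSSI at follow-up without a usable number, the plan allows imputed values of 0 or below. The share of such draws is an assumption, not a figure from the documents: roughly 11% to 33% untransformed and 2% to 20% on a log scale. A single value such as one in five is mid-range for untransformed draws only.

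The number of youths affected cannot be derived. The undercount applies to arm means. A reader might infer a bias of known direction in the treatment effect, but the documents do not support that: its sign depends on which arm has more unusable answers. The rate ratio is nearly unchanged with equal rates, and moves by about 0% to 2% with an assumed 5% against 15%.

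The same reasoning does not carry over to suicidal ideation (SI). That count asks for days on which thoughts lasted beyond a few minutes, while its screen is described as any SI in the past 3 months. A youth with only fleeting thoughts could screen positive and correctly report 0 days.

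**What to change.** Make three changes.
1. In the primary outcome definition, state how a blank or non-numeric count is coded when the screen is yes, and how such an answer is told apart from random text that leads to exclusion.
2. Under Imputing Data, state that a youth who screens positive for NSSI at follow-up but lacks a usable count is imputed from responders with a positive count, by a two-part model or by matching on baseline count and condition. Do not rely on the unconditional normal model, on the screening answer as a predictor alone, or on simple truncation at 1, which overshot in step 6. Keep unconditional imputation for youths without a screening answer.
3. Make the NSSI count box numeric-only, with a prompt when it is left empty. The plan states that no data have been collected, so this can still be done and would prevent most of the problem at source.

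Do not set a minimum of 1 for the SI day count. The cost is a few sentences, one survey setting and slightly more imputation code.

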### ***Secondary Dependent Variables***

**Likelihood of Future NSSI.** Likelihood of future NSSI will be measured immediately pre- and post-intervention. We will evaluate self-reported likelihood of future non-suicidal self-injury immediately post-intervention—comparing participants in the Project SAVE SSI versus supportive therapy SSI control conditions, and controlling for pre-intervention likelihood score. An item from the Self-Injurious Thoughts and Behaviors Interview-R (Fox et al., 2020) will assess participants’ beliefs about the likelihood of future non-suicidal self injury on a 5-point Likert Scale (range = 0 to 4; 0 = “not at all”; 4 = “extremely”).

**SI Frequency in the Past 3 Months.** We will compare past 3-month SI frequency at 3-month follow-up—for participants assigned to the Project SAVE SSI versus supportive therapy SSI (i.e. control condition). At pre-intervention and 3-month follow-up time points, participants will indicate “how many days did they have thoughts about killing themselves for more than a few minutes” in the past 3 months in an open-response text box. Notably, in the present study’s survey flow, this question is displayed following display logic—such that participants endorsing zero history of SI in the past 3 months (via a previous question) skip to the end of the question block and are not prompted to answer our frequency outcome question. For these individuals, we will impute a past 3-month frequency value equal to 0 (as they have endorsed zero SI in the previous 3 months in the earlier question). More information about how we will handle very large numbers (i.e. outliers) for this outcome is reported below (see “Outliers and Exclusions” section; “Winsorizing Outliers” subsection).

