***Testing Hypothesis 2: Do teenagers in the Project SAVE SSI condition endorse lower frequency of SI in the past 3 months—relative to teenagers in the active control program?***

First, we create our secondary outcome variable (i.e. frequency of SI in the past 3 months) by imputing values equal to 0 for participants who endorsed zero SI in the previous 3 months in an earlier question. See “SI Frequency in the Past 3 Months” under the key dependent variables section for more details.

Next, we will determine whether a Poisson regression, a negative binomial regression, a zero-inflated Poisson regression, or a zero-inflated negative binomial regression is most appropriate for analyzing our past 3-month frequency outcome (count variable). To do this, we will run all four models, conducting model fit tests to compare AIC values, BIC values, and raw scores for each regression. If all three indices agree (i.e. select the same “best” model of the four possible), we will interpret the results of that regression. If they do not agree (i.e. select different “best” models from the four possible), we will report the results from each of the selected models.

Regardless of model type, we will enter pre-intervention past 3-month frequency of SI as a covariate, and treatment condition as a predictor, of past 3-month frequency of SI at follow-up in the chosen regression(s). We will consider a *p* value of less than .05 for the treatment condition coefficient (in favor of the Project SAVE SSI) as a significant effect of the Project SAVE treatment on frequency of SI in the past 3-months.

***Testing Hypothesis 3: Do teenagers in the Project SAVE SSI condition endorse lower frequency of NSSI in the past 3 months—relative to teenagers in the active control program?***

We will follow the same procedures for hypothesis 2 but replacing “SI frequency in the past 3 months” with “NSSI frequency in the past 3 months.”

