### ***Winsorizing Outliers***

We will winsorize outliers in our two count variables of interest (past 3-month frequency of NSSI at pre-intervention and follow-up) before running tests for hypothesis 2 and 3. Outliers will be defined as values above the 95th percentile for the variable in question, calculated using the Winsorize() function in the DescTools package in R (Singnorell et al., 2020, <https://cran.r-project.org/web/packages/DescTools/DescTools.pdf>).

[project.org/web/packages/DescTools/DescTools.pdf](https://project.org/web/packages/DescTools/DescTools.pdf)); flagged outliers will be replaced with the 95th percentile value.

**How many observations will be collected or what will determine the sample size? No need to justify decision, but be precise about exactly how the number will be determined. (optional)**

The final sample size for *collected* data will be  $N = 500$  randomized participants (250 per condition) who meet our type 1 inclusion criteria (i.e. who are not excluded by type 1 exclusion criteria outlined in the above section). The total number of participants who provide *usable* data will then be determined by the number of participants who meet our type 2 inclusion criteria (i.e. who are not excluded by type 2 exclusion criteria outlined above). Therefore, the present study will have a maximum of 500 participants, with a final sample size determined by the number of participants meeting our type 2 inclusion criteria specified above.

**Other. Anything else you would like to pre-register? (e.g., secondary analyses, variables collected for exploratory purposes, unusual analyses planned?) (optional)**

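### Suicidal-ideation days cannot exceed about 92, yet the plan sets no valid range and sends large answers to a 95th-percentile cap unrelated to that limit

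*Combined protocol and SAP*

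**What the plan says.** All references are to the combined protocol and SAP.

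- **Secondary Dependent Variables.** The SI item asks "how many days did they have thoughts about killing themselves for more than a few minutes", and the answer is given "in the past 3 months in an open-response text box". It is asked before the intervention and at 3-month follow-up. Youths who report no SI in the window skip the item and are assigned 0. For large answers the section points forward: "More information about how we will handle very large numbers (i.e. outliers) for this outcome is reported below", naming the winsorizing subsection.
- **Winsorizing Outliers.** "Outliers will be defined as values above the 95th percentile for the variable in question", and "flagged outliers will be replaced with the 95th percentile value". The rule is to be applied before Hypotheses 2 and 3, but the variables it names are self-injury (NSSI) only: "We will winsorize outliers in our two count variables of interest (past 3-month frequency of NSSI at pre-intervention and follow-up".
- **Testing Hypothesis 2.** For the SI outcome, "we will determine whether a Poisson regression, a negative binomial regression, a zero-inflated Poisson regression, or a zero-inflated negative binomial regression is most appropriate". Baseline SI frequency is the covariate.
- **Type 2 Exclusions.** Random text, copied text and similar quality failures lead to exclusion. Nothing is said about a number outside the possible range.
- **Primary Dependent Variable.** NSSI is a number of times, which has no calendar limit.

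No section states a maximum, a field check or a rule for an SI answer such as 200.

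**The concern.** Three months contain 89 to 92 days, so a number of days in that window has a known ceiling. An answer of 200 is therefore not an unusual value but an error, and an answer of 90 is not an outlier but a plausible report of near-daily ideation. A sample percentile cannot tell these apart. It was a reasonable device for NSSI, which is open-ended, but it has been carried over to an outcome for which a natural validity rule exists.

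The H2 estimate would then depend on how many youths mistype or misread the question. Depending on that share, errors enter the model as real data or valid answers are altered. Once data are in hand, any decision about answers above 92 would be post hoc.

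**Working it through.** **1. Inputs.** From the documents: N = 500 randomized, 1:1, so 250 per arm; cap at the sample 95th percentile; four count models; baseline SI as covariate. By calendar arithmetic: ceiling of 89 to 92 days, with 92 used here. The plan gives no power figure, effect size, SI distribution, dropout rate or data-error rate for H2, so there is no stated figure to reproduce and everything in step 4 is assumption.

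**2. When does the cap exceed 92?** Only when more than 5% of entries are impossible. Of 500, 0.05 × 500 = 25, so 26 or more are needed. With per-entry error rate q, the chance is P(X ≥ 26), X ~ Binomial(500, q):

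| q | 2% | 3% | 4% | 5% | 6% | 8% |
|---|---|---|---|---|---|---|
| P | 0.0000 | 0.006 | 0.11 | 0.45 | 0.80 | 0.99 |

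The denominator includes the assigned zeros. If 25% of youths were zeros (an assumption), 5% of all entries would be 0.05 / 0.75 = 6.7% of typed answers.

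**3. The cases for one variable.**

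- *More than 5% impossible:* the cap is above 92. Entries above the cap are lowered only to another impossible value, and no valid answer is touched.
- *Some, but fewer than 5%:* the cap normally falls within the valid range. Impossible entries become high but credible answers, and valid answers above the cap are lowered too.
- *None:* up to 25 of 500 valid answers can be lowered. In simulated clean data 23 to 24 were, with median caps of 20, 55 and 84 days in the low, mid and high scenarios below.
- *Winsorizing section read literally:* SI is not capped and every impossible value stays.

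**4. Effect on power (simulation).** Days ~ Binomial(92, p), with logit(p) normal, plus structural zeros. Mean, SD and zero share were: low −2.8, 1.2, 20%; mid −1.5, 1.5, 20%; high −0.3, 2.0, 15%. Assumed effects were 0.35, 0.45 and 0.60 on the logit scale. There were 250 per arm, no dropout, two-sided unadjusted 0.05 and 250 replicates, so the Monte Carlo SE is about √(0.7 × 0.3 / 250) = 0.03. The plan was represented by winsorizing SI at baseline and follow-up, then choosing negative binomial or zero-inflated negative binomial by AIC. The Poisson models were left out because the data are strongly overdispersed. The range-check columns drop entries above 92 and do not winsorize. The bounded model is a fractional logit with robust SE.

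| Impossible, of non-zero answers | Scenario | Plan | Range check, same count models | Range check, bounded model |
|---|---|---|---|---|
| 0% | low | 0.72 | 0.70 | 0.67 |
| 0% | mid | 0.74 | 0.76 | 0.74 |
| 0% | high | 0.78 | 0.78 | 0.84 |
| 2% | low | 0.61 | 0.69 | 0.60 |
| 2% | mid | 0.68 | 0.79 | 0.77 |
| 2% | high | 0.72 | 0.74 | 0.82 |
| 8% | low | 0.25 | 0.64 | 0.58 |
| 8% | mid | 0.29 | 0.65 | 0.62 |
| 8% | high | 0.39 | 0.66 | 0.69 |

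With 20% structural zeros, 8% of non-zero answers is at most 0.08 × 0.80 = 6.4% of all entries, above the 5% threshold. Likewise 2% is at most 1.6%, well below it, so the losses in the 2% rows come from recoding, not from impossible values surviving. With no true effect and clean data, rejection was 0.03–0.04 (plan), 0.03–0.05 (count models, no winsorizing) and 0.03–0.06 (bounded model).

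**5. Side effect.** The 95th percentile was not a whole number in roughly 20–60% of simulated datasets. The plan states no rounding, though its models are for counts; values were rounded here before fitting.

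**The case against.** The strongest reply is that the percentile rule already blunts gross errors. Impossible values survive it only above a 5% error rate, the documents give no error rate, and at 3% the chance of crossing the threshold is 0.006. Rewriting up to 5% of values is simply what winsorizing does, and the cap is common to both arms. Random text is screened separately, and H2 is secondary. All of this is correct. It limits the size of the problem but does not supply a valid range, and recoding an impossible answer to a credible one is still wrong at low error rates.

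Three stronger readings are tempting, and the documents do not support them.

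- *Impossible values stay and valid answers are cut together.* For one variable these exclude each other: the first needs a cap above 92, the second a cap below it. They never occurred together in a simulated dataset.
- *Near-daily ideators in particular are cut.* This depends on the distribution. With median caps of 20 or 55 days, most altered answers need not be near-daily; only the high scenario (84 days) fits.
- *Unbounded count models cost H2 power and should be replaced.* The advantage of a bounded model changes sign with the assumed data. With clean data it was 0.67 v 0.72, 0.74 v 0.74 and 0.84 v 0.78 (bounded v plan), although effects were generated on the logit scale, which favours the bounded model. Other assumptions widen the gap: against a plain negative binomial the bounded model gained 4, 19 and 28 points, and with beta-binomial days it also did better. The documents give no SI distribution to choose between these.

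**Conclusion.** The point holds as one about data validity. A day count with a ceiling of about 92 has no stated valid range, and the only rule offered for large answers is unrelated to that ceiling and, on its literal wording, may not cover SI at all. No reading of the plan handles an out-of-range answer correctly.

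The size depends on the error rate, which is unknown. Under the assumed distributions, a range check with the planned count models gained 2 to 11 points of power with 2% impossible non-zero answers and 27 to 39 points with 8%. With clean data the difference was within simulation error (−2 to +2 points), and the harm is then the needless alteration of about 23 to 24 valid answers in 500. The literal, uncapped reading was not simulated.

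A general loss of power from the count models is not established. Because H2 is secondary and the remedy is cheap, this is a change that should be made, not one on which the trial's main conclusion turns.

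**What to change.** 1. At baseline and follow-up, replace the SI text box with a whole-number field that accepts 0 to 92 and prompts for re-entry. State that any remaining out-of-range entry is set to missing and handled by the planned imputation. The Imputing Data section already lists predictors for SI at follow-up, but its opening list of variables omits SI, so add it there.
2. State that the 0–92 limit replaces percentile winsorizing for SI, and correct the Winsorizing Outliers section and the forward reference in Secondary Dependent Variables so that they agree. The percentile rule for NSSI is not affected.
3. Optionally, add a bounded model for H2 (beta-binomial, or fractional logit with robust SE, out of 92 days) as a sensitivity analysis with the same covariate and condition terms, without claiming that it is generally more powerful.

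The cost is one survey-field setting and a few sentences. The Data Collection Status entry says that no data have been collected, so the field check can still prevent the problem. If the optional model is added, its effect is reported as an odds ratio or a difference in days, alongside the rate ratio from the count models.
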